1.1 Introduction

Sudden cardiac death (SCD) is a major cause of mortality throughout the world, accounting for approximately 300,000 deaths per year in the United States.¹ SCD accounts for about 50% of all heart related deaths. Studies of patients who suffer SCD suggest that ventricular tachyarrhythmias are the dominant cause of this rapid terminal event although asystole due to heart block or sinus arrest can account for approximately 10-15% of the sudden deaths. However, these are most often electrical signs of a dying heart or electro-mechanical dissociation. The introduction of the implantable cardiac defibrillator (ICD) in the 1980s resulted in subsequent clinical trials showing a significant reduction in SCD with ICD therapy in at-risk cardiac patients.

However,²⁻⁴ not all high-risk patients are candidates for the ICD for a variety of reasons. These are: transient nature of the high-risk for SCD; patients who do not meet current guideline indications for an ICD;⁵ high-risk cardiac patients who had previously received an ICD but had it removed because of complications or malfunction; patients who refuse an ICD; age-related factors; and a variety of other medical and ethical considerations.

The use of automatic external defibrillator (AED) in acute cardiac arrest in the home, school, workplace, airplanes, and locations where there is a high density of people such as airports and sporting events has limited effectiveness in saving lives.⁶ Successful resuscitation with utilization of the AED is dependent on a short time-interval of just a few minutes between the witnessed cardiac arrest and the AED intervention. The rate of successful resuscitation for out-of-hospital cardiac arrest with the AED with full recovery to a normal neurologic state is not more than 8%.

The Wearable Cardioverter-Defibrillator (WCD) gives the patient's physician time to assess the long-term arrhythmic risk in cases when the risk of life-threatening arrhythmias may only be temporary and to make appropriate plans. Thus, the WCD can be used as a risk stratification tool. It provides continuous arrhythmia monitoring, detection of life-threatening ventricular arrhythmias, and provides automatic defibrillation within a minute of detection of the potentially fatal ventricular tachyarrhythmia, unless the patient withdraws the shock delivery. The safety and effectiveness of the WCD in saving lives has been documented in several publications including the first report in 1998,⁷ WEARIT/BIROAD study in 2004,⁸ and the US and German experience report in 2013.⁹⁻¹²

Currently, there is only one approved WCD device on the world-wide market. This is the LifeVest®, produced by ZOLL, Pittsburgh, PA, USA. During the past few years, there has been an increased use of the WCD to more than 100,000 patients (personal information from ZOLL, Pittsburgh, PA, USA) having a spectrum of at-risk cardiac conditions, with use of the WCD averaging over 21 hours per day for periods of 1 to 6 months, or even longer.

The WCD is a therapeutic option, listed along with implantable cardioverter-defibrillators (ICDs), in the ACC/AHA/ESC Guidelines for the Management of Patients with Ventricular Arrhythmias and the Prevention of Sudden Cardiac Death¹³. It is also a Class I recommendation in the International Society for Heart and Lung Transplantation Guidelines for the Care of Cardiac Transplant Candidates¹⁴.

1.4 Rationale and Aims of the study

LifeVest is a wearable cardioverter defibrillator (WCD) that has been recently approved for reimbursement by the HAS. LifeVest has obtained coverage for 4 indications: (i) implantable cardiac defibrillator (ICD) removal due to cardiac device infections, (ii) a bridge to heart transplantation, (iii) in the early post-MI period with left ventricular (LV) dysfunction (LVEF <30%), (iv) and a recent coronary revascularization with LV dysfunction (LVEF < 30%). There is no current comparator to LifeVest. In France, patients at high risk for sudden cardiac arrest (SCD) and waiting for heart transplant or ICD are hospitalized or discharged home without any particular ECG monitoring. LifeVest has been demonstrated to automatically detect and terminate rapid ventricular arrhythmias. Introduction of LifeVest into the current patient management would definitely improve the clinical outcomes and benefit the patients with temporary risk of SCD. The use of LifeVest was shown to be effective in protecting patients against SCD in the United States. However, the clinical impact of using LifeVest in France remains unassessed. Therefore, this post-market study in France will provide efficacy and safety data for the reimbursement dossier renewal before September 2018.

Identification and description of the investigational device

The Wearable Cardioverter-Defibrillator (WCD) [LifeVest ®] is an external defibrillator, guided by an algorithm to detect ventricular tachyarrhythmic events, recorded by non-adhesive ECG electrodes (two leads). The WCD delivers up to 5 biphasic, high-voltage electrical shocks unless shock delivery is withheld intentionally by a conscious patient. The WCD comprises also a continuous ECG monitoring system, which transmits ECG data and other information (such as recorded arrhythmic events and alerts, details of the shock delivery episode, appropriate WCD use, daily wearing time, correct ECG monitoring,

battery charging and electrode connection/electrode noise) directly from the LifeVest to a central ECG and data server in the USA, Pittsburgh. The patient's physician is able to check the history of recorded arrhythmic events, details of the shock delivery episode, appropriate WCD use, daily wearing time and correct ECG monitoring via a password protected web-accessed to the ECG and data server.

The WCD has CE certification and is FDA approved since 2002.

2. Justification for the design of the investigation

In general, patients considered having high, long term risk of sudden arrhythmic death (SCD) receive implantable cardioverter-defibrillators (ICD).

Risk assessment in patients that are candidates for ICD therapy is difficult and time consuming, though. In order to bridge the time period necessary to identify the patient who will need an ICD or in whom ICD therapy is unnecessary, a tool is mandatory that protects the patient during this time period from dying suddenly and to provide continuous ECG monitoring which is necessary for the risk assessment.

The device that is able to fulfill these characteristics is the wearable cardioverter-defibrillator (WCD). The WCD has CE certification and is FDA approved since 2002. Currently, only observational studies with the WCD are available. Prospective randomized studies in patients that are already considered carrying a high risk of sudden death are difficult, if not impossible to perform, mainly due to ethical reasons.

Currently available data with the WCD demonstrate that the WCD is safe and effective. Detected ventricular tachyarrhythmias are terminated with the first shock in 98% of all cases; inappropriate defibrillator discharges (not occurring on sustained VT or VF) may occur in <1% per month of WCD wearing⁹.

3. Risks and benefits of the investigation

Patients participating in the post-market clinical follow-up study in France will have neither additional risks due to participation in the study compared to clinical routine care nor individual benefits, because of its purely observational character.

4. Objectives and hypotheses of the investigation

4.1 Objectives

a) Primary Objective:

1. **Appropriate shocks** as measured by shocks delivered for adjudicated sustained ventricular tachycardia (VT) or ventricular fibrillation (VF) episodes.
2. **Inappropriate shocks** as measured by shocks delivered for all episodes that are not adjudicated sustained VT or VF episodes.

The frequency and rate of appropriate and inappropriate shocks will be measured. The risk of receiving an inappropriate shock will be analyzed. The risk of not receiving appropriate shocks when necessary will also be analyzed.

b) Secondary Objectives

1. **Overall survival** as measured by the ratio of the number of patients that are alive at the end of the use of the WCD to the total population of patients prescribed the LifVest.
2. **Quality of life relative to health state** as measured through the administration of a patient quality of life survey. This survey has been used previously in a published study of patient quality of life.

5. Design of the investigation

5.1 General

5.1.1 Description of investigation

France post marketing protocol is an observational study of patients with a prescribed WCD during the time of risk assessment for future potential ICD therapy. Patients who are prescribed a WCD will be asked to participate in the prospective cohort of the study. Patients who have already completed use of LifeVest before start of the study in the corresponding study site can also be asked to consent for use of their clinical data to be included in the retrospective cohort of the study. The retrospective cohort of patients will be analysed separately compared to prospectively included study patients for any variables that are not available for both cohorts, such as the patient survey. Mean WCD wearing time is anticipated to be three months. However, some indications for wearing the WCD may be longer (up to 6 months) or shorter (only one month). For patients who are listed for heart transplantation, the wearing time is scheduled until heart transplantation is performed, or an ICD will be implanted.

5.1.2 Description of the measures to be taken to minimize or avoid bias, including randomization and blinding/masking

There is no randomization of patients enrolled into the study. All consenting patients with a routinely prescribed WCD in the study participating centers will be evaluated, regardless of the length of WCD wearing, including patients who have already completed use of LifeVest before start of the study in the corresponding study site.

The selection bias is limited by the protocol comprehensiveness. There will be no selection, the study will be proposed to all patients receiving LifeVest. In addition, all centres performing implantation of the device will be asked to participate. "Non-participants" will be described.

The attrition bias is also limited (non-existent) as at the end of LifeVest utilization, all material provided to the patient should be returned systematically. Furthermore, the patients follow- up is completely identical to the routine clinical practice. This means that we don't expect to have any difference between the data collected retrospectively and those collected prospectively. However, only patients included prospectively will be asked to complete the quality of life questionnaire.

The prospective cohort of patients will be analysed separately for variables not available for the patients in the retrospective cohort, such as the patient survey.

Patients who have worn WCD for at least 8 days (i.e. longer than 1 week) will be evaluated separately in an "on-treatment" efficacy analysis, because it is assumed from clinical experience that the WCD wear-

ing time will only for those patients be long enough to reliably compare their long-term outcome in a cohort of patients who have had the WCD for several months (even six or more months in some indications).

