5.2 Subjects

Study population will consist of patients at high risk for SCD and receiving LifeVest as a bridge therapy to heart transplantation, to ICD or to improvement of LV function.

5.2.1 Inclusion criteria for subject selection.

- Patients receiving a LifeVest prescription in clinical routine for the following indications:
 - a) implantable cardiac defibrillator (ICD) removal due to cardiac device infections,
 - b) a bridge to heart transplantation,
 - c) in the early post-MI period with left ventricular (LV) dysfunction (LVEF <30%),
 - d) a recent coronary revascularization with LV dysfunction (LVEF < 30%).
- Patients who have given their consent to participate.

This includes also those patients who have already completed use of LifeVest before start of the study in the corresponding study site (retrospective inclusion).

5.2.2 Exclusion criteria for subject selection.

There are no exclusion criteria for this study other than if the patient does not provide informed consent to participate. All patients prescribed a LifeVest will be invited to participate. All patients that were previously prescribed a LifeVest before the start of this study will also be invited to participate by allowing access to their retrospective medical information.

5.2.3 Criteria and procedures for subject withdrawal or discontinuation.

A low rate of lost-to-follow up is expected since the LifeVest is rented to patients and should be returned to ZOLL by the end of the prescription. In case a patient is lost to follow up, the CepiDC a French database for automated coding of causes of death, will be interrogated to report if the patient is dead or alive, and if dead the cause of death.

All patients enrolled into the study can withdraw at any time regardless of the reason. Patients may withdraw consent for use of data and exit the study at any time without prejudice to further treatment.

Patients who have given consent to participate in the study but had the WCD for less than 8 days will be evaluated separately, but not withdrawn.

5.2.4 Participating centers and point of enrolment:

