5.4 Monitoring plan

Authorized, qualified representatives of the sponsor will accomplish on-site monitoring during the study. The accuracy and completeness of core CRF data of a sufficient number of patients will be checked on site against source documents. Details will be given in a risk based monitoring plan.

Quality management will assure that medical data are subject of continuous plausibility checks and data cleaning. The primary outcome parameters consist of follow-up and arrhythmic event raw data which are directly transmitted in clinical routine from the WCD device to a central database to which the treating physician has access via an internet platform enabling him to review any potential arrhythmic event

detected by the device. These data are not modified by human interactions, thus being *per se* valid and do not require source data verification.

6. Statistical considerations and methods

This is a nonrandomized, multicenter observational study. All consecutive LifeVest patients will be asked to participate. Demographic data will be reported on all consenting patients. Thus, all patients in this study will receive LifeVest treatment. Descriptive statistics will be used to report major clinical characteristics of consenting patients, and incidence and frequency of appropriate and inappropriate shocks.

For the overall survival rate calculation, the population of reference will correspond to the total number of patients enrolled who were prescribed the LifeVest.

Standard methods will be used to calculate adjusted survival rates. Kaplan Meier survival curves will be used to report total mortality and wear time. The time to event and census are defined here after.

All reasons for therapy discontinuation will be reported in tabular form.

Event	Decision	Event date or census date
Occurrence of the event	Not censored	Date of the event occurrence
No event and patient followed until the study end	Censored	Date of WCD withdrawal
Lost-to-follow-up	Censored	Date of the last visit or last contact

It is common to use a significance threshold of 5%. This will be applied in this study.

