The protocol will be submitted for review to the Advisory Committee on Information Processing in Research in the Field of Health (Comité Consultatif sur le Traitement de l'Information en Matière de Recherche dans le Domaine de la Santé - CCTIRS), then for approval to the French Data protection Authority (Nationale Informatique et Liberté - CNIL) before any data collection.

The participating investigators receiving financial compensation for the conduct of the study, the protocol and the financial agreement will be sent for review to the French Medical Council (Conseil National de l'Ordre des Médecins - CNOM) in accordance with the Article L.4113-6 of the French Code of Public Health.

10.3 Statement specifying that the study protocol will be sent for comment to the EC

In accordance with the French legislation (Articles L.1121-1 and following of the French Code of Public Health), given that the physician-patient relationship is not changed and that no examination or consultation is specific to the observatory, the study will not be subject to the opinion of a French Ethics Committee (Comité de Protection des Personnes, CPP).

10.4 Statement specifying the type of insurance that shall be provided for subjects, if appropriate.

No insurance is required because this study is purely observational. All medical treatment is decided and provided in clinical routine. The clinical routine insurance of the product will therefore cover all risk.

11. Informed consent process

Before entering into the study, information about the intention and nature of the study will be provided to each potentially eligible patient by the prescribing responsible physician of each participating center. Each patient will be informed about the use of his medical data in the clinical study according to the requirements data privacy regulations, i.e. consent to processing medical data of the patient to a central scientific database. Sufficient time will be allowed for the information to be read and for questions to be asked. Only subjects able to give their informed consent will be enrolled in this clinical study.

The patient must be told that withdrawal of informed consent to use their data in the clinical study is possible at any time, without stating a reason and without prejudice, and does not cause any disadvantages.

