4.2 Secondary study objectives

1. Overall survival as measured by the ratio of the number of patients that are alive at the end of the use of the WCD to the total population of patients prescribed the LifeVest.
2. Quality of life relative to health state as measured through the administration of a patient quality of life survey. This survey has been used previously in a published study of patient quality of life.

LifeVest has been recently approved for reimbursement by the HAS. LifeVest has obtained coverage for 4 indications: (i) implantable cardiac defibrillator (ICD) removal due to cardiac device infections, (ii) a bridge to heart transplantation, (iii) in the early post-MI period with left ventricular (LV) dysfunction (LVEF <30 %), (iv) and a recent coronary revascularization with LV dysfunction (LVEF < 30 %). There is no current comparator to LifeVest. In France, patients at high risk for sudden cardiac arrest and waiting for heart transplant or ICD are hospitalized or discharged home without any particular ECG monitoring. LifeVest has been demonstrated to automatically detect and terminate rapid ventricular

arrhythmias. Introduction of LifeVest into the current patient management would definitely improve the clinical outcomes and benefit the patients with temporary risk of SCD. The use of LifeVest was shown to be effective in protecting patients against SCD in the United States. However, the clinical impact of using LifeVest in France remains unassessed. Therefore, this post-market study in France will provide efficacy and safety data for the reimbursement dossier renewal before September 2018.

5. Sample size and Power

This study is a post-inscription study designed to describe all patients treated by LifeVest in a comprehensive way. Thus this study will be proposed to all patients receiving LifeVest.

No sample size calculation has been planned. All patients accepting to participate will be included.

The LifeVest device is commercialized in France since approximatively 3 years, the number of subjects has been estimated based on the sales and the foreseen participation rate.

It was estimated that approximately 1,700 patients will receive LifeVest in clinical routine between May 2015 and April 2018 (300 patients first year, 520 patients second year and 880 patients third year of marketing) in France. After obtaining all regulatory approvals, the study started in August 2016.

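### To the extent retrospective patients are enrolled, pooling them into the ITT survival and death analyses understates on-WCD mortality, because they can consent only after finishing WCD use alive

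*Combined protocol and SAP*

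**What the plan says.** **Entry.** Protocol 5.1.1 states: "Patients who have already completed use of LifeVest before start of the study in the corresponding study site can also be asked to consent". Consent is an inclusion criterion in Protocol 5.2.1 ("Patients who have given their consent to participate"). Protocol 11 adds: "Only subjects able to give their informed consent will be enrolled in this clinical study". Death is one of the listed reasons for end of use in Protocol 5.3.1.4.

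**Estimand.** SAP 4.2 defines overall survival as the ratio of patients "alive at the end of the use of the WCD to the total population of patients prescribed the LifeVest". Protocol 6 narrows the denominator: "the population of reference will correspond to the total number of patients enrolled who were prescribed the LifeVest". SAP 11 uses the total ITT population for the ratio, and plans Kaplan-Meier curves and Cox models under the same ITT heading. SAP 9.2 tabulates deaths on ITT, including deaths on the device.

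**Pooling.** SAP 6.1 says the ITT set may include patients who finished use before their site started. It separates the cohorts only for variables not held in both, with the survey as the example.

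**Bias statement.** Protocol 5.1.2 says: "There will be no selection, the study will be proposed to all patients receiving LifeVest". It also says the authors do not expect "any difference between the data collected retrospectively and those collected prospectively". Survival as a condition of retrospective entry is not mentioned.

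**The concern.** A retrospective patient is approached after use has ended and must consent in person. Someone whose use ended in death before the site opened cannot do that. Every retrospective enrollee is therefore alive at end of use by construction. In the Protocol 6 event table such a patient can only fall in the row "No event and patient followed until the study end", censored at WCD withdrawal.

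The stated target is survival among everyone prescribed the device. The pooled estimate instead mixes a cohort in which deaths can occur with one in which they cannot. The error has a known direction, in favour of the device. Overall survival is the first secondary objective, and the study is meant to supply efficacy and safety data for reimbursement renewal.

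**Working it through.** **1. The plan's own figures.** Forecast participants: 1,110 x 50% = 555, stated as about 550. Precision of a shock rate at n = 550, from 1.96 x sqrt(p(1 - p)/n): 0.83 points at 1% and 1.82 points at 5%. This reproduces the stated 0.8 and 1.8. The plan gives no corresponding figure for survival.

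**2. Formula.** Let nP and nR be the prospective and retrospective counts, s = nR/(nP + nR), and m the prospective on-WCD mortality. Deaths are m x nP from the prospective cohort and 0 from the retrospective one. Crude pooled mortality = m x nP/(nP + nR) = m(1 - s). Equal underlying mortality in the two cohorts is what lets m stand for the true rate. The understatement is then s in relative terms, not s percentage points.

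**3. Kaplan-Meier.** Event-free retrospective patients enlarge each risk set. With similar wear times the estimated hazard falls by about the factor (1 - s). In a simulation with constant hazard, 90-day mortality of 1% to 5%, and wear fixed at 90 days or exponential (mean 90, capped at 180), relative understatement was 9.8% to 10.0% at s = 10% and 24.6% to 25.0% at s = 25%.

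**4. Illustrative share.** Inputs:
- Yearly sales forecast 300, 520, 880, total 1,700 from May 2015 to April 2018; 1,110 of these from August 2016 (Protocol 5.2.9 and 6.1, SAP 5).
- Start in August 2016 (same sections) or enrolment from March 2017 (Protocol 5.2.10).
- Mean wear of three months (Protocol 5.1.1); about 1,200 enrolled (SAP 5).
- *Assumption:* the 50% participation rate, stated for users after study start, also applies to earlier users.

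Only patients who had completed use belong in the count. At 520 per year and three months' wear, about 520 x 3/12 = 130 would still be wearing the device at study start.

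| Basis | Users before start | Completed use | x 50% | Share of 1,200 |
|---|---|---|---|---|
| August 2016, even accrual | 300 + 520 x 3/12 = 430 | 300 | 150 | 12.5% |
| August 2016, by subtraction | 1,700 - 1,110 = 590 | 460 | 230 | 19.2% |
| March 2017, even accrual | 300 + 520 x 10/12 = 733 | 603 | 302 | 25.1% |

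The first two rows differ because 430 + 1,110 = 1,540, not 1,700. The forecast does not fit even accrual.

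**5. Result, m(1 - s).**

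| Assumed true mortality | s = 12.5% | s = 19.2% | s = 25.1% |
|---|---|---|---|
| 1% | 0.88% | 0.81% | 0.75% |
| 3% | 2.6% | 2.4% | 2.2% |
| 5% | 4.4% | 4.0% | 3.7% |

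At 3% the shift is 0.38, 0.58 or 0.75 points. The 95% half-width of the pooled estimate, 1.96 x sqrt(p(1 - p)/1200) at the pooled p, is 0.90, 0.87 or 0.84. The shift is smaller than sampling error in all three cases, but it is systematic and does not shrink with sample size at a fixed share.

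**6. Existing safeguards.** The CepiDC query (Protocol 5.2.3) is for patients lost to follow-up, not for people never enrolled. The non-inclusion registry (Protocol 5.2.4) holds demographics, indication and reason. Nothing feeds it into the survival estimate.

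**The case against.** **The share may be nil.** SAP 6.1 says only that such patients may be included, and no count is given. This stands, and it makes the point conditional. Against it, Protocol 5.2.2 says earlier users will be invited.

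**The illustration combines inputs from different forecasts.** This also stands. The 50% rate belongs to the sales forecast, while 1,200 arose from recruitment above expectation. With 150 retrospective patients, the other 1,050 would be 95% of the forecast 1,110. Only the formula rests on the documents.

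**Stronger readings a reader might infer, which the documents do not support:**
- *All users before study start are retrospective* (430, 590 or 733, giving about 18%, 25% or 31% of 1,200). Protocol 5.1.1 requires completed use; those still wearing the device can consent and later die on it.
- *The share should be taken of 550.* That figure was built from post-start users only, so it is not a pooled denominator.
- *The Cox subgroup hazard ratios are biased.* That needs the retrospective share to differ by subgroup, which is not shown. An even spread lowers the baseline hazard without necessarily distorting the ratios.
- *The no-difference statement in Protocol 5.1.2 is false.* It follows a remark about routine follow-up and can be read as being about data collection.

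**Mitigation and descriptive purpose.** The registry may make some early deaths visible as reasons for non-inclusion, if it covers earlier users. That helps disclosure but leaves the estimate unchanged. A descriptive figure must still describe its stated population.

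**Conclusion.** The point holds in conditional form. To the extent retrospective patients are enrolled, the pooled crude survival ratio, Kaplan-Meier mortality and deaths tables understate on-WCD mortality. The relative understatement is the retrospective share for the crude ratio, and approximately that for Kaplan-Meier.

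This rests on four conditions: no route into the retrospective cohort other than the patient's own consent (the consent pages were not in the text available, so another route cannot be fully excluded); equal underlying mortality in the two cohorts; for Kaplan-Meier, similar wear times; and pooling as SAP 6.1 and 11 are worded. The direction is firm. The size cannot be fixed from the documents: the illustrated shares of about 12% to 25% could be lower, including zero, or higher with later site starts.

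Prospective documentation also starts at consent (Protocol 5.2.4), so deaths between prescription and consent may be missed there and the prospective figure may itself be somewhat low. That does not justify adding a cohort with no possible deaths. A reader should not infer from this that the primary shock results are materially affected; the point does not rest on them.

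**What to change.** - **SAP 11 and the deaths part of SAP 9.2:** make the prospective cohort the primary set for overall survival and deaths. Report the retrospective cohort separately, with its size, labelled as conditional on survival to consent. Show pooled ITT as a sensitivity analysis.
- **Secondary refinement:** where consent follows activation, use the consent date as delayed entry in the time-to-event analyses. The documents do not give the size of this effect.
- **Protocol 5.1.2:** qualify the no-selection statement to acknowledge that retrospective inclusion requires survival to consent. Amending the no-difference sentence is optional.

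**Cost.** SAP wording, a cohort flag, and a consent date that already marks the start of documentation. Intervals widen slightly: at 3% mortality, 1.96 x sqrt(0.03 x 0.97/n) is 1.03, 1.07 or 1.12 points on 1,050, 970 or 898 prospective patients, against 0.97 on 1,200. The reported survival figure will be less favourable if the retrospective share is not zero. No patient data are discarded. If no retrospective patients were enrolled, the results do not change.
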